Bayer has recently conducted a retrospective cohort study on prescription patterns of NOACs in NVAF patients in UK general practice using a combination of the THIN and CPRD databases. Amongst patients without an apparent indication for dose reduction, the reduced dose was prescribed in approximately 30% of patients receiving apixaban and 10% of patients receiving rivaroxaban in the new-users of both agents (Study 19330, unpublished data). We therefore hypothesize that in the UK, the higher than expected rates of reduced dose apixaban use as compared to the Phase III trials will exhibit higher rates of stroke and systemic embolism versus warfarin than rivaroxaban, which appears to be prescribed at the reduced dose less frequently. Also, patients with renal impairment receiving standard dose are at increased risk of bleeding. Although, warfarin use has certainly decreased in the recent years, this drug remains the main oral anticoagulant used in the UK. It has also been the active comparator of choice in most clinical trials of NOAC (O'Dell et al.) and in our opinion constitutes an ideal reference drug for these analyses. Both the standard and the reduced dose of NOACs have been compared to warfarin in clinical trials and shown to be as safe and effective as warfarin. Warfarin itself does not have dose-reduction requirements however the dose needs to be adjusted to maintain INR between 2.0-3.0. Rivaroxaban and apixaban are most widely used NOACs in the UK whereas the use of dabigatran is low and declining since 2014 (Study 19330, unpublished data). Also, the appropriate and inappropriate use of dabigatran is difficult to estimate due to a multiple criterion in the label for dose reduction which is difficult to assess using secondary data sources. Risk of major bleeding especially GI bleeding for NOACs is extensively studied, and our research question is to study the effect of under-dosing on the risk of stroke (effectiveness outcome). However, to also study the other side of the balance which is bleeding, we included ICH because it is an event comparable to stroke in terms severity. GI bleeding is an acute event, usually followed by complete recovery in vast majority of patients. In terms of the balanced outcomes, it is important to take account of the severity of the disease events prevented and caused by the intervention, and not just the frequencies of the events. Thus GI bleeds, which are sometimes severe, are acute events usually followed by recovery without sequelae, while strokes and ICH can leave residual physical and/or cognitive impairments in those who survive, and may require complex and lifelong interventions. Therefore, GI Bleeding is not included as an outcome in this study.

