9.5 Study size

Study 19330 (unpublished data) conducted in UK identified 8,629 initiators of apixaban and 12,353 initiators of rivaroxaban among patients with NVAf from 2011 through 2016 within the THIN database. A study conducted in UK between 1 December 2012 and 31 October 2014 using CPRD, reported 10,218 naïve users of warfarin (Johnson et al. 2016). With an additional year up to 2017, the expected numbers of Rivaroxaban, Apixaban and Warfarin users will be greater than numbers reported above. Thus, assuming the study will include at least 10,000 initiators of each study drug and annual rates of intracranial hemorrhage, ischemic stroke, and all-cause mortality of 1%, 2%, and 4%, we expect the study to identify at least a total of 900, 1800, and 3600 events respectively. In case only 50% of initiators continue drug use at index date (i.e. current users at index date), we should be able to detect, with a statistical power greater than 80%, odds ratios of 1.5 associated to current use of each study drugs for intracranial haemorrhage, odds ratios of 1.3 for ischemic stroke, and odds ratios of 1.2 for all-cause mortality.

Regarding the daily dose analyses, power calculation will depend largely on the percentage of individuals we found in each daily dose category. For instance in, if we assume that 30% of current users of apixaban will use a reduced dose (2.5mg Bid), half of them appropriately, for the comparison between “appropriate” and “inappropriate” reduced dose of apixaban we would be able to detect odds ratios of 3.5 when exploring intracranial hemorrhage, odds ratios of 2.4 for ischemic stroke, or odds ratios 1.8 for all-cause death. On the other hand for the comparison between “inappropriate” reduced dose of apixaban versus warfarin current use, if the assumptions described above hold, we should be able to detect with a power of at least 80% odds ratios of 2.3, 1.8, and 1.6 for ICH, IS, and all-cause mortality respectively. Note that all these calculations have assumed a two-sided type I error of 5%.

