controls” in such a way that the frequency of matching factors (age categories, sex, and calendar year) among selected controls at their random dates matches that of the cases at the index date (i.e. frequency-matched controls). In other words, if 2% of cases are males, belong to the age category 40-49 and have 2010 as year of their index date, then 2% of controls are males, belong to the age category 40-49 and have 2010 as year of their random date. Under our study design of incidence density sampling, the odds ratio (OR) is an unbiased estimator of the incidence rate ratio (RR) (Rothman 2012). Unconditional logistic regression models will be used to obtain OR estimates of OAC use adjusted by baseline variables described above and OAC use at index date. The model will include all covariates described in section 9.3.3 in the logistic regression model (fully-adjusted model). Additionally, and depending on the number of cases ascertained, we could explore simpler models based on either change-in-estimate or statistical significance approaches. Specifically the following analyses will be performed for each outcome:

- a) OAC daily dose: We will use the daily dose criteria described in 9.3.1.2 to classify current users of rivaroxaban and apixaban and compare with warfarin as follows:

Rivaroxaban

- Overall Rivaroxaban (both doses) vs warfarin
 - o 20mg OD – No dose reduc. criteria – Appropriate vs warfarin
 - o 20mg OD – Dose reduction criteria – Inappropriate vs warfarin
 - o 15mg OD - No dose reduc. criteria – Inappropriate vs warfarin
 - o 15mg OD – Dose reduction criteria – Appropriate vs warfarin
 - o Overall Appropriate use vs warfarin

Apixaban

- o Overall Apixaban (both doses) vs warfarin
 - 5mg Bid - No dose reduc. criteria – Appropriate vs warfarin
 - o 5mg Bid – Dose reduction criteria – Inappropriate vs warfarin
 - o 2.5mg Bid - No dose reduc. criteria – Inappropriate vs warfarin
 - o 2.5mg Bid – Dose reduction criteria – Appropriate vs warfarin
 - o Overall Appropriate use vs warfarin
- b) Outcomes will also be analysed in the sub-group of diabetes and by renal function (CKD-EPI) (creatinine clearance or serum creatinine as described in the label of the respective NOAC). Since renal function is taken into account in this classification, individuals without

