renal function values available (expected to be less than 5%) will be excluded from these analyses. Using warfarin current use as the reference category, we will estimate the risk of the study outcomes associated to the rivaroxaban and apixaban daily dose categories described above.

- c) OAC duration: We will use the duration variable described in section 9.3.3. to compare different drug durations of current use with non-use of each study drug. Additionally we will compare “Continuers” and “Discontinuers/Switchers” with non-use of each study drug.
- d) Stratified analysis: The above described analyses will also be conducted separately for naïve, and non-naïve patients at start date.

Comparisons will be done based on adjusted point estimates and confidence intervals obtained from multivariable regression.

We will describe the patterns of use of study medication or other NOACs (edoxaban/dabigatran) after intracranial hemorrhage events, and ischemic events that occurred during the study period. The current hypothesis is that a patient will restart with anticoagulation within 1-3 months of an event.

Strategy for handling missing data

As a general strategy, no data imputation strategies will be applied to supplement missing data. However, missing values may occur in a small proportion. In this case, individuals with missing values will be kept in the analysis and a separate category will be created for missing values of that variable.

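### The dose analyses give no planned estimate for under-dosing or for apixaban relative to rivaroxaban, although Section 7 poses both questions

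*Protocol*

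**What the plan says.** **Question.** Sections 4 and 7, explaining why GI bleeding is left out, say "our research question is to study the effect of under-dosing on the risk of stroke (effectiveness outcome").

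**Hypothesis.** Section 7 expects that UK apixaban use, with its higher share of reduced dosing, "will exhibit higher rates of stroke and systemic embolism versus warfarin than rivaroxaban, which appears to be prescribed at the reduced dose less frequently". Section 4 words the same expectation as apixaban against rivaroxaban directly.

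**Objectives.** Section 8.1 asks for rivaroxaban and apixaban, each versus warfarin, by dose and by whether the dose agrees with the label.

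**Analysis.** Section 9.7(a) will "classify current users of rivaroxaban and apixaban and compare with warfarin as follows". Six contrasts follow for each NOAC: overall, four dose-by-criteria cells, and overall appropriate use. The under-dosed apixaban cell, for example, is "2.5mg Bid - No dose reduc. criteria – Inappropriate vs warfarin". The text printed under item (b) sets the reference: "Using warfarin current use as the reference category, we will estimate the risk of the study outcomes associated to the rivaroxaban and apixaban" daily-dose categories. Item (c) compares durations of use with non-use, so it is not a dose contrast.

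**Study size.** Section 9.5 gives detectable odds ratios for one dose comparison without warfarin, appropriate against inappropriate "reduced dose of apixaban we would be able to detect odds ratios of 3.5 when exploring intracranial hemorrhage", with 2.4 for ischaemic stroke and 1.8 for death.

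**The concern.** The effect of under-dosing is the difference between reduced and standard dose in patients who do not meet the reduction criteria. Each of those two groups is planned only against warfarin. The hypothesis about the two NOACs is a comparison of two odds ratios, and each of those is likewise planned only against warfarin.

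A reader of the report would have to compare odds ratios by eye. Two intervals that share a reference do not give the interval for their ratio, because the covariance of the two coefficients is needed. If the ratio is computed later, it will have been chosen after the 12 odds ratios were seen. That is best avoided in a study funded by the maker of one NOAC that expects the other to do worse.

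The comparison powered in 9.5 does not fill the gap. It holds the dose constant and varies the patients.

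**Working it through.** **1. Contrasts.** Rivaroxaban has 6 and apixaban has 6, so 12 in total, all against warfarin. None compares reduced with standard dose of one NOAC, and none compares the two NOACs.

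**2. Inputs, all from 9.5 unless marked.**
- 10,000 initiators per drug and 900 / 1,800 / 3,600 events (intracranial haemorrhage / ischaemic stroke / death). For stroke, 30,000 × 2% × 3 years = 1,800; the 3 years is implied, not stated.
- 50% are current users, so each drug's current users are 1/6 of all subjects.
- 30% of current apixaban users are on the reduced dose, half appropriately. Each half is 0.15/6 = 0.025 of subjects.
- Two-sided 5% level, 80% power.
- Controls per case: not stated. Assumed 1:1, with 4:1 shown.
- Share of current apixaban users on an appropriate standard dose: assumed 50–70%.

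**3. Formula.** For categories A and B with subject shares fA and fB, and m controls per case:
- cases n1 = D(fA + fB), controls n0 = m·n1
- p0 = fA/(fA + fB), p1 = OR·p0/[1 + p0(OR − 1)], p̄ = (p1 + m·p0)/(1 + m)
- power = Φ{[|p1 − p0| − 1.96·√(p̄(1 − p̄)(1/n1 + 1/n0))] / √(p1(1 − p1)/n1 + p0(1 − p0)/n0)}, solved for OR at 0.80.

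**4. The plan's own figures, 1:1.** Appropriate versus inappropriate reduced apixaban, for stroke: n1 = 1,800 × 0.05 = 90, p0 = 0.50; OR 2.37 gives p1 = 0.703 and power 80%. For the three outcomes the result is 3.54 / 2.37 / 1.82, against the stated 3.5 / 2.4 / 1.8. Inappropriate reduced apixaban versus warfarin, for stroke: n1 = 1,800 × (0.025 + 0.1667) = 345, p0 = 0.130; OR 1.78 gives p1 = 0.211 and power 80%. The three outcomes give 2.20 / 1.78 / 1.52, within the stated 2.3 / 1.8 / 1.6. The 1:1 assumption therefore reproduces the plan's dose figures.

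**5. The missing contrasts, same inputs.**

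| Contrast (stroke) | Cases | Detectable OR, 1:1 | 4:1 |
|---|---|---|---|
| Inappropriate reduced apixaban vs warfarin (planned) | 345 | 1.78 | 1.57 |
| Inappropriate reduced vs appropriate standard apixaban, 70% share | 255 | 1.82 | 1.60 |
| Same, 50% share | 195 | 1.87 | 1.64 |
| Current apixaban vs current rivaroxaban | 600 | 1.38 | 1.29 |

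**6. Why the interval needs the covariance.** In a crude analysis with equal odds and 1:1 controls, each cell contributes 2/cases to the variance of a log odds ratio. For apixaban versus rivaroxaban with 300 stroke cases each (1,800/6), the variance is 2/300 + 2/300 = 0.0133, SE 0.115. Treating the two warfarin odds ratios as independent counts the 300-case warfarin cell twice: 0.0133 + 2 × 2/300 = 0.0267, SE 0.163, which is 41% too large. For reduced versus standard apixaban (45 and 210 cases), the correct SE is √(2/45 + 2/210) = 0.232, against 0.259.

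**7. Restricting warfarin to the same criteria status.** Assume 20–30% of warfarin users meet the criteria. The criteria-positive reduced-apixaban cell then faces a reference of 0.033–0.05 of subjects instead of 0.167. At 1:1 its detectable odds ratio rises from 1.78 to 2.01–2.18 for stroke, and from 2.20 to 2.66–3.06 for intracranial haemorrhage. For the criteria-negative cell the stroke figure moves only to 1.80–1.82.

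**The case against.** The planned contrasts are exactly those of Section 8.1, and Section 7 argues for warfarin as the reference. The research-question sentence appears in the rationale for leaving out GI bleeding, and the Annex 2 checklist marks hypotheses to be tested as not applicable. Section 7 also puts its hypothesis on the warfarin scale, so both component odds ratios are planned. All of this stands, and the warfarin contrasts should stay. It does not supply the two ratios or their intervals.

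A reader might infer that under-dosing cannot be estimated at all. The protocol does not support that: if all categories share one model, both ratios follow from planned coefficients. A statistical analysis plan could add them, but the protocol itself fixes the contrast list and the reference, and it names neither a single model nor a ratio.

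A reader might also infer that pooling warfarin users with and without criteria seriously biases the results. The documents give no basis for a size. The model adjusts for age, eGFR, frailty and BMI (body weight itself is not listed). Section 9.7(b) also analyses by renal function, with eGFR bands of 30–49 and 15–29 that match the rivaroxaban creatinine-clearance cut-points in 9.3.1.2. Moreover, any distortion from the shared reference is common to both no-criteria cells of a NOAC, and cancels in reduced versus standard dose.

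Finally, prescribers chose the reduced dose for patients without criteria for some reason, so the under-dosing contrast carries its own confounding. That is true and should be stated with the result.

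**Conclusion.** The concern holds as a mismatch between the question in Sections 4 and 7 and the outputs of 9.7(a), not as a departure from Section 8.1. No pre-specified estimate with a confidence interval answers either the under-dosing question or the apixaban–rivaroxaban hypothesis. The one comparison without warfarin that 9.5 powers answers neither, and 9.7 does not list it. Lack of precision is not the reason: the detectable stroke odds ratio is about 1.82–1.87 against 1.78 for the planned warfarin contrast. These figures rest on the inputs of 9.5, an assumed 1:1 control ratio, and an assumed 50–70% of current apixaban users on an appropriate standard dose. It should be fixed, but it does not invalidate the planned warfarin comparisons.

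**What to change.** 1. Keep the 12 warfarin contrasts. State in 9.7(a) that the dose-by-criteria categories of both NOACs enter one model per outcome, with current warfarin use as the common reference.
2. Add, each with a confidence interval from that model: (i) reduced versus standard dose of the same NOAC among patients without dose-reduction criteria, as the main under-dosing estimate, with the mirror contrast among patients with criteria; (ii) the apixaban/rivaroxaban ratio of odds ratios.
3. In 9.5, replace the appropriate-versus-inappropriate figures with those for contrast (i), about 1.82–1.87 for ischaemic stroke under the assumptions above, and state the control ratio.
4. Use a warfarin reference restricted to the same criteria status as a sensitivity analysis only, given its loss of precision in the criteria-positive cells.

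The cost is protocol wording and a few more contrasts from the same data. Contrast (i) remains open to confounding by the prescriber's choice of dose, and the protocol should say so.

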9.8 Quality control

Standard operating procedures at research centre will be used to guide the conduct of the study. These procedures include internal quality audits, rules for secure and confidential data storage, methods to maintain and archive project documents, quality control procedures for programming, standards for writing analysis plans, and requirements for senior scientific review.

All programming written by the executing researcher will be reviewed independently by a senior researcher. All key study documents, such as study reports, will undergo quality control and senior scientific review.

Privacy issues will be addressed and respected at each stage of the study. All analyses and reporting will be done on appropriately de-identified data. The Sponsor will not receive any patient or provider identifiable information from CEIFE at any time. We will abide by the Guidelines for Good Pharmacoepidemiology Practices (ISPE n.d.). The study protocol is dependent on approval by a Scientific Research Committee (SRC) that review studies performed in THIN

9.9 Limitations of the research methods

- Given the nature of real-world data, missing data are likely to be present in a minority of instances. As a general strategy, no data imputation strategies will be applied to supplement missing data. However, missing values may occur in a small proportion. In this case, individuals with missing values will be kept in the analysis and a separate category will be created for missing values of that variable.
- Only prescriptions captured in THIN dataset will be available. Medications prescribed at hospital will not be captured nor will over the counter medications (OTC). This might induce some exposure misclassification that we expect to be non-differential. This might introduce to some bias towards the null in study estimates. While bias towards the null is generally considered as conservative in effectiveness analyses, it is considered as anticonservative in safety analyses (tends to conclude treatment strategies are similar even if they are not). We should take this into account when interpreting study results.
- Incomplete data concerning medication compliance: drug use is based on prescriptions written by the treating physician, but no information is available to confirm if the drug was actually taken by the patient (common to virtually any computerized clinical database).
- There may be some missing data if GPs may not enter the hospitalization data however we expect that the vast majority of GPs will record information on hospitalization into THIN.
- Some lifestyle variables such as smoking, BMI and alcohol consumption is not consistently recorded for all patients.
- The results from observational analyses should be interpreted with care, as in the presence of remaining confounding, any findings cannot simply be attributed to use of study drugs.

9.10 Other aspects

Not applicable

10. Protection of human subjects

The study will be conducted in accordance with Good Pharmacoepidemiology Practices.. In this investigation we will use a medical record linkage database where the information of patients is anonymized and there is no need to obtain informed consent from patients. The study protocol is dependent on approval by a Scientific Research Committee (SRC) for studies performed in THIN Centro Español de Investigación Farmacoepidemiológica (CEIFE) will comply with all applicable data protection, security and privacy laws, rules and regulations with respect to the collection, production, use, processing, storage, transfer, modification, deletion, and/or disclosure of any information related to this study under this Agreement. CEIFE will ensure that information is not disclosed or transferred to any third party not mentioned in this protocol. CEIFE will ensure that

appropriate technical and organizational measures are taken to protect information against accidental or unlawful destruction or accidental loss or alteration, or unauthorized disclosure or access and against all other unlawful forms of processing. CEIFE will store the Database used to perform this study at the premises of CEIFE. Privacy issues will be addressed and respected at each stage of the study. All analyses and reporting will be done on appropriately de-identified data and only in aggregate form.

As per the EMA Guideline on Good Pharmacovigilance Practices (Module VI–Management and reporting of adverse reactions to medicinal products), for non-interventional study designs that are based on secondary use of data, individual reporting of adverse reactions is not required (European Medicines Agency n.d.).

11. Management and reporting of adverse events/adverse reactions

As per the EMA Guideline on Good Pharmacovigilance Practices (Module VI–Management and reporting of adverse reactions to medicinal products), for non-interventional study designs that are based on secondary use of data, individual reporting of adverse reactions is not required. Reports of adverse events/reactions will be summarized in the study report (European Medicines Agency 2012).

12. Plans for disseminating and communicating study results

At least one manuscript based on the findings from this project will be submitted for publication to a peer-review journal.

Annex 1: List of stand-alone documents

None

Annex 2: ENCePP checklist for post-authorization safety study (PASS) protocols

ENCePP Checklist for Study Protocols (Revision 3)

Study title:
Safety and Effectiveness of Rivaroxaban and Apixaban compared to warfarin in non valvular atrial fibrillation patients in the routine clinical practice in the UK
 SiERRA UK

Study reference number: 20343

Section 1: Milestones	Yes	No	N/A	Section Number
1.1 Does the protocol specify timelines for				6
1.1.1 Start of data collection ¹				
1.1.2 End of data collection ²				
1.1.3 Study progress report(s)				
1.1.4 Interim progress report(s)				
1.1.5 Registration in the EU PAS register				
1.1.6 Final report of study results.				

Comments:

Section 2: Research question	Yes	No	N/A	Section Number
2.1 Does the formulation of the research question and objectives clearly explain:				7, 8
2.1.1 Why the study is conducted? (e.g. to address an important public health concern, a risk identified in the risk management plan, an emerging safety issue)				
2.1.2 The objective(s) of the study?				
2.1.3 The target population? (i.e. population or subgroup to whom the study results are intended to be generalised)				
2.1.4 Which hypothesis(-es) is (are) to be tested?				
2.1.5 If applicable, that there is no a priori hypothesis?				

¹ Date from which information on the first study is first recorded in the study dataset or, in the case of secondary use of data, the date from which data extraction starts.

² Date from which the analytical dataset is completely available.

Comments:

Section 3: Study design	Yes	No	N/A	Section Number
3.1 Is the study design described? (e.g. cohort, case-control, cross-sectional, new or alternative design)				9.1
3.2 Does the protocol specify whether the study is based on primary, secondary or combined data collection?				9.1
3.3 Does the protocol specify measures of occurrence? (e.g. incidence rate, absolute risk)				
3.4 Does the protocol specify measure(s) of association? (e.g. relative risk, odds ratio, excess risk, incidence rate ratio, hazard ratio, number needed to harm (NNH) per year)				9.7
3.5 Does the protocol describe the approach for the collection and reporting of adverse events/adverse reactions? (e.g. adverse events that will not be collected in case of primary data collection)				11

Comments:

Section 4: Source and study populations	Yes	No	N/A	Section Number
4.1 Is the source population described?				9.1
4.2 Is the planned study population defined in terms of:				
4.2.1 Study time period?				9.1, 9.2.2
4.2.2 Age and sex?				
4.2.3 Country of origin?				
4.2.4 Disease/indication?				
4.2.5 Duration of follow-up?				
4.3 Does the protocol define how the study population will be sampled from the source population? (e.g. event or inclusion/exclusion criteria)				9.2.3

Comments:

Section 5: Exposure definition and measurement	Yes	No	N/A	Section Number
5.1 Does the protocol describe how the study exposure is defined and measured? (e.g. operational details for defining and categorising exposure, measurement of dose and duration of drug exposure)				9.3.1
5.2 Does the protocol address the validity of the exposure measurement? (e.g. precision, accuracy, use of validation sub-study)				

Section 5: Exposure definition and measurement		Yes	No	N/A	Section Number
5.3	Is exposure classified according to time windows? (e.g. current user, former user, non-use)				9.3.1, 9.3.3
5.4	Is exposure classified based on biological mechanism of action and taking into account the pharmacokinetics and pharmacodynamics of the drug?				

Comments:

Section 6: Outcome definition and measurement		Yes	No	N/A	Section Number
6.1	Does the protocol specify the primary and secondary (if applicable) outcome(s) to be investigated?				9.3.2
6.2	Does the protocol describe how the outcomes are defined and measured?				9.3.2
6.3	Does the protocol address the validity of outcome measurement? (e.g. precision, accuracy, sensitivity, specificity, positive predictive value, prospective or retrospective ascertainment, use of validation sub-study)				9.3.2.1
6.4	Does the protocol describe specific endpoints relevant for Health Technology Assessment? (e.g. HRQoL, QALYs, DALYS, health care services utilisation, burden of disease, disease management)				

Comments:

Section 7: Bias		Yes	No	N/A	Section Number
7.1	Does the protocol describe how confounding will be addressed in the study?				9.7
	7.1.1. Does the protocol address confounding by indication if applicable?				
7.2	Does the protocol address:				
	7.2.1. Selection biases (e.g. healthy user bias)				
	7.2.2. Information biases (e.g. misclassification of exposure and endpoints, time-related bias)				9.3.2.1, 9.7
7.3	Does the protocol address the validity of the study covariates?				

Comments:

Section 8: Effect modification		Yes	No	N/A	Section Number
---------------------------------------	--	------------	-----------	------------	-----------------------

Section 8: Effect modification	Yes	No	N/A	Section Number
8.1 Does the protocol address effect modifiers? (e.g. collection of data on known effect modifiers, sub-group analyses, anticipated direction of effect)				

Comments:

--

Section 9: Data sources	Yes	No	N/A	Section Number
9.1 Does the protocol describe the data source(s) used in the study for the ascertainment of:				
9.1.1 Exposure? (e.g. pharmacy dispensing, general practice prescribing, claims data, self-report, face-to-face interview)				9.4
9.1.2 Outcomes? (e.g. clinical records, laboratory markers or values, claims data, self-report, patient interview including scales and questionnaires, vital statistics)				9.4
9.1.3 Covariates?				9.4
9.2 Does the protocol describe the information available from the data source(s) on:				
9.2.1 Exposure? (e.g. date of dispensing, drug quantity, dose, number of days of supply prescription, daily dosage, prescriber)				9.3.1
9.2.2 Outcomes? (e.g. date of occurrence, multiple event, severity measures related to event)				9.3.2
9.2.3 Covariates? (e.g. age, sex, clinical and drug use history, co-morbidity, co-medications, lifestyle)				9.3.3
9.3 Is a coding system described for:				
9.3.1 Exposure? (e.g. WHO Drug Dictionary, Anatomical Therapeutic Chemical (ATC) Classification System)				9.3.1
9.3.2 Outcomes? (e.g. International Classification of Diseases (ICD)-10, Medical Dictionary for Regulatory Activities (MedDRA))				9.3.2
9.3.3 Covariates?				9.3.3
9.4 Is a linkage method between data sources described? (e.g. based on a unique identifier or other)				

Comments:

--

Section 10: Analysis plan	Yes	No	N/A	Section Number
10.1 Is the choice of statistical techniques described?				9.7
10.2 Are descriptive analyses included?				9.7
10.3 Are stratified analyses included?				9.7

Section 10: Analysis plan	Yes	No	N/A	Section Number
10.4 Does the plan describe methods for adjusting for confounding?				9.7
10.5 Does the plan describe methods for handling missing data?				9.7
10.6 Is sample size and/or statistical power estimated?				

Comments:

Section 11: Data management and quality control	Yes	No	N/A	Section Number
11.1 Does the protocol provide information on data storage? (e.g. software and IT environment, database maintenance and anti-fraud protection, archiving)				9.6
11.2 Are methods of quality assurance described?				9.8
11.3 Is there a system in place for independent review of study results?				

Comments:

Section 12: Limitations	Yes	No	N/A	Section Number
12.1 Does the protocol discuss the impact on the study results of:				9.9
12.1.1 Selection bias?				
12.1.2 Information bias?				
12.1.3 Residual/unmeasured confounding? (e.g. anticipated direction and magnitude of such biases, validation sub-study, use of validation and external data, analytical methods)				
12.2 Does the protocol discuss study feasibility? (e.g. study size, anticipated exposure, duration of follow-up in a cohort study, patient recruitment)				

Comments:

Section 13: Ethical issues	Yes	No	N/A	Section Number
13.1 Have requirements of Ethics Committee/ Institutional Review Board been described?				10
13.2 Has any outcome of an ethical review procedure been addressed?				
13.3 Have data protection requirements been described?				10

Comments:

Section 14: Amendments and deviations	Yes	No	N/A	Section Number
14.1 Does the protocol include a section to document amendments and deviations?				5

Comments:

Section 15: Plans for communication of study results	Yes	No	N/A	Section Number
15.1 Are plans described for communicating study results (e.g. to regulatory authorities)?				
15.2 Are plans described for disseminating study results externally, including publication?				12

Comments:

Name of the main author of the protocol: _____

Date: 13/August/2018

Signature: _____

